1. BACKGROUND & STUDY RATIONALE

Left atrial appendage and stroke

Stroke, particularly cardioembolic stroke, is a frequent and serious complication of atrial fibrillation. Previous reports have shown that the left atrial appendage (LAA) is the source of embolus in the majority of patients who suffer this complication.

Traditionally, oral anticoagulant medications (OAC) have been used to reduce the risk of embolic stroke in patients with atrial fibrillation. Warfarin has been the most frequently used agent in this regard. Recently dabigatran, rivaroxaban, and apixaban have been introduced for the same purpose. These novel agents have potential advantages over warfarin; they are less susceptible to dietary and drug-drug interactions. Due to their mechanism of action, routine INR testing is not necessary. For these reasons, their use is increasing, and many physicians report increased compliance with anticoagulation with the newer regimens. However, there is a significant patient population who continue to be at elevated bleeding risk with the use of any OAC. Patients with clinically significant bleeding, intracranial hemorrhage, and patients with a prohibitively high risk of falls often do not receive OAC therapy, and remain at elevated risk for stroke.

Left atrial appendage management

There are at the present three methods of addressing management of the LAA aside from oral anticoagulant therapy: Surgical excision, external ligation of the appendage, and internal occlusion of the left atrial appendage.

Surgical excision is generally performed during a concomitant cardiac procedure. The proximal portion of the appendage is closed with sutures or staples, and the trabeculated portion is removed. This has been shown to reduce risk of stroke after cardiac surgery. Surgeons note that this can result in significant bleeding, and other alternatives have recently been employed.

Internal occlusion is accomplished via a transseptal approach. The Watchman® device (Boston Scientific, Inc.) has completed its second controlled trial. The results of the PROTECT-AF trial were presented at the Heart Rhythm Society Scientific Sessions in Denver, CO on May 9, 2013, and seemed to show non-inferiority, and in some endpoints, superiority to, medical therapy with warfarin. The Amplatzer Cardiac Plug® trial was discontinued by the sponsor, and no public announcement has been made regarding restarting the trial. For both of these devices, OAC therapy is required for at least 45 days post-procedure. OAC therapy is required for a greater period of time if LAA closure is incomplete.

Two devices have been used in multiple centers in the US for ligation of the LAA, the AtriClip® (AtriCure, Inc) and the SentreHeart Lariat® (SentreHeart, Inc). The AtriClip® is a surgical device approved for LAA closure *in patients undergoing other cardiac procedures*. Deployment of the AtriClip® has not received an FDA indication as a stand-alone procedure. The Lariat® device is approved for soft tissue ligation, without a specific indication for LAA closure.

2. STUDY OBJECTIVES

Objectives

1. The primary aim is to assess the outcome of patients undergoing left atrial appendage ligation or closure with the SentreHeart Lariat® device as a stand-alone procedure at the participating centers
2. Secondary aims include assessment of adverse events and successful LAA closure rates

Hypothesis

Closure of the left atrial appendage with the SentreHeart Lariat® is reasonable alternative to reduce the risk of stroke in patients with an elevated bleeding risk with the use of any OAC and in whom this risk is prohibitive.

3. STUDY DESIGN

The study is a multi-center, prospective outcomes registry. The study cohort will comprise all consecutive patients who undergo lone left atrial appendage closure using the SentreHeart Lariat® at the investigational centers and should consist of up to 50 patients. Patients will undergo follow-up visits at 7 days, 90 days, and 180 days post procedure.

4. STUDY POPULATION

The study cohort will consist of up to 50 patients who are candidates for LAA closure in whom oral anticoagulation is contraindicated.

4.1 Inclusion Criteria

- Patients aged ≥ 18 years
- Patients able and willing to provide informed consent
- Documentation of atrial fibrillation or atrial flutter
- Clinical decision by the subject's physician that the patient is at risk for embolic stroke, and OAC is contraindicated (using the assessment outlined in Table 1)
- HAS-BLED score ≥ 3
- CHADS₂-VASC score ≥ 3 , OR CHADS₂-VASC of 2 if physician provides justification for procedure
- Anatomy favorable for deployment of the SentreHeart Lariat®

4.2 Exclusion Criteria

- Medically unable to provide informed consent
- Previous cardiothoracic surgery
- Patient is a candidate for catheter or surgical ablation
- Need for concomitant cardiac surgery procedure
- Thrombus in the left atrial appendage or left atrium
- Pregnancy

4.3 Inclusion of special, vulnerable or high risk populations

4.3.1 Elderly

Atrial fibrillation and atrial flutter are most common in the aging population and would account for the inclusion of this population. Ample time will be allotted to assure that this population has the opportunity to carefully read the consent, share this information with family members, and discuss the objective of the study along with any risks/benefits that may be expected. Subjects will have all of their questions answered before signing the consent and taking part in the study.

5. ENROLLMENT & STUDY PROCEDURES

Subjects evaluated for left atrial appendage closure will be screened for inclusion and consented prior to their procedure. During clinical evaluation of the patient, the physician investigator will assess those items described in Table 1. If the anatomy is favorable for placement of the Lariat® device, the procedure will be performed at one of the participating centers. If anatomy is not favorable, the patient will be excluded from the study and managed using best care practices by his or her physician. Please note, at The Heart Hospital Baylor Plano, the Lariat device is only available to patients participating in the study.

Subjects consented will be tracked by the study team and will be considered enrolled in this study at the time of the start of their left atrial appendage closure procedure. All subjects that are consented who do not undergo left atrial appendage closure with SentreHeart Lariat® will be considered screen failures. Any patients that have a failed attempt at left atrial appendage closure with SentreHeart Lariat® will be tracked through their index hospitalization for safety; their study follow up will be complete at the time of discharge.

The invasive procedure for placement of the study devices will proceed according to standard interventional techniques, as already in place at the participating centers. Patients undergoing the Lariat® procedure will be administered colchicine 0.6 mg po twice daily for a minimum of three days preoperatively, and 30 days postoperatively. (This dose may be adjusted for renal function or intolerance).

5.1 Baseline

The following information will be collected for all subjects enrolled:

1. History and Physical
2. Cardiac medication list
3. Labs: Creatinine, BUN
4. CHADS₂-VASC score
5. HAS-BLED
6. All females of childbearing age will have a urine or serum pregnancy test within 24 hours prior to procedure
7. Cardiac computed tomography angiography (CCTA) will be used to evaluate if subjects' anatomy is favorable for deployment of the CentreHeart Lariat®

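### The only specified pregnancy test comes after protocol colchicine has started, so an unrecognised pregnancy would be exposed for at least about 36 to 48 hours before it could be detected

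*Combined protocol and SAP*

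**What the plan says.** Section 4.2 lists pregnancy as an exclusion, with no test method and no timing. The check appears as item 6 of the Section 5.1 baseline list: "All females of childbearing age will have a urine or serum pregnancy test within 24 hours prior to procedure".

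Section 5 sets the drug schedule. Patients having the procedure are "administered colchicine 0.6 mg po twice daily for a minimum of three days preoperatively, and 30 days postoperatively". It adds that "This dose may be adjusted for renal function or intolerance".

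Section 5 ties screening and consent to the procedure, not to the first dose: "Subjects evaluated for left atrial appendage closure will be screened for inclusion and consented prior to their procedure". The baseline list also includes a history and physical.

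No other pregnancy test is specified. The visit matrix in Section 6 has no row for one, and the Table 1 screening tool has no item for one.

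**The concern.** An eligibility check protects a subject only if it comes before the interventions that the protocol imposes. Here the first such intervention with a stated lead time is colchicine, and its start falls outside the window in which the pregnancy test must be done. A site that follows the text exactly gives the drug first and verifies the exclusion afterwards.

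What is at stake is the safety of a small and possibly empty group: women of childbearing age with a pregnancy that neither they nor the clinician knows about. If the test were positive, the procedure would not go ahead and Section 5 would class the woman as a screen failure. The matrix begins adverse event assessment at the procedure and schedules no visit for screen failures, so the exposure would have no scheduled safety assessment in the study.

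**Working it through.** The plan gives no figure for this interval, so there is none to reproduce. The check is a timeline.

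**Inputs from the documents**
- Test window (Section 5.1): 0 to 24 h before the procedure, so the earliest allowed test is at −24 h.
- Dose (Section 5): 0.6 mg twice daily, for a minimum of three days before the procedure.

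**Assumptions**
- Twice daily means one dose every 12 h.
- Three days is read in two ways. In A it means 72 elapsed hours, with the first dose at −72 h. In B it means six doses with the last at the procedure, so the first dose is at −60 h.
- A dose counts only if it falls strictly before the test.

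**Formulas**, with S the hours from first dose to procedure and T the hours from test to procedure
- Lead time = S − T.
- Doses before the test = the number of times S, S − 12, S − 24, … that are greater than T.
- Amount = doses × 0.6 mg.

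**Earliest allowed test (T = 24)**
- A: 72 − 24 = 48 h; doses at −72, −60, −48 and −36 h = 4; 4 × 0.6 = 2.4 mg.
- B: 60 − 24 = 36 h; doses at −60, −48 and −36 h = 3; 3 × 0.6 = 1.8 mg.

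**Latest allowed test (T = 0)**
- A: 72 h; 6 doses; 6 × 0.6 = 3.6 mg.
- B: 60 h; 5 doses; 5 × 0.6 = 3.0 mg.

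**Variants**
- Earlier start, which the three-day minimum allows. For example, S = 120 and T = 24 gives 120 − 24 = 96 h and 8 doses (−120 to −36 h).
- Dose cut to once daily, taken as every 24 h, with T = 24. A gives −72 and −48 h; B gives −60 and −36 h. Each is 2 doses, over the same 48 and 36 h.

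The drug precedes the test in every case. The hours are a minimum under each reading. The dose count is not, because a permitted adjustment can lower it.

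**Could such a woman enter?** Section 4.1 admits patients from age 18, and neither score needs an age point. By Table 1, a woman with prior stroke, bleeding history and antiplatelet use scores as follows:
- CHADS₂-VASC: stroke 2 + female sex 1 = 3.
- HAS-BLED: stroke 1 + bleeding 1 + drugs 1 = 3.

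Both meet the entry threshold of 3. This shows possibility only, since she must also meet the other criteria in Sections 4.1 and 4.2.

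**After the fix**, a negative test is required before the first dose. Doses taken before any test fall from 3 to 4 (or more) to 0.

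**The case against.** The case against giving this weight is substantial, and much of it stands.

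- **Harm.** The documents do not say that this exposure is harmful. Section 12.1 lists procedural risks and nothing about colchicine, and the only dosing caution in Section 5 concerns renal function and intolerance. A reader might infer a demonstrated fetal hazard, but the documents do not support that. They support a flaw in sequence.
- **Numbers.** The group may be empty. Section 4.3.1 notes that "Atrial fibrillation and atrial flutter are most common in the aging population", and entry also needs high stroke and bleeding scores, contraindicated anticoagulation, no candidacy for ablation and favorable anatomy. No count of women of childbearing age is given.
- **Existing layers.** A known pregnancy can be excluded at the history and physical. The specified test does precede the invasive step and formal enrollment, which Section 5 dates to the start of the procedure. Nothing forbids an earlier test. A reader might infer that the pregnancy exclusion goes unchecked in general, but that would be wrong: the gap concerns unrecognised pregnancy only.
- **Imaging.** A reader might also infer that the baseline CCTA comes before the test. The protocol does not date the CCTA against the test or against consent, so that inference is unsupported and forms no part of this point.

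These objections limit the size of the point. They do not remove it, because the order of drug and test follows from the text, and an optional earlier test is not a requirement.

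**Conclusion.** The point holds as a low-severity safety fix. Under the minimum course, protocol colchicine precedes the earliest allowed pregnancy test by at least about 36 to 48 hours. The figure of 3 to 4 doses rests on 12-hourly dosing without adjustment and on the two readings of three days; it should not be read as a fixed range. Few if any of the up to 50 subjects would be affected. No endpoint, estimate or analysis depends on it. The reason to act is that the protocol already judged a pregnancy test necessary, and moving the first check ahead of the first protocol drug costs almost nothing.

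**What to change.** In Section 5.1, require a negative urine or serum pregnancy test in females of childbearing age shortly before the first colchicine dose, for example within 24 hours. The stated interval matters: without one, a negative test from weeks earlier would comply and could miss a later conception. Keep the existing test in the 24 hours before the procedure as the last gate before the invasive step. Add a pregnancy-test row to the Section 6 matrix showing both time points.

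The cost is a sentence in Section 5.1, a row in the matrix, and one extra inexpensive test for a few subjects.

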5.2 Left Atrial Appendage Closure Procedure

The following information will be collected at the time of Procedure

1. TEE evidence of LAA closure
2. Angiographic confirmation of LAA closure
3. Presence/absence of pericardial effusion
4. Amount (# ml) of pericardial drainage
5. X-ray exposure
6. Total amount of contrast used
7. Adverse Events Assessment
8. Assessment

5.3 Follow-up Visits

5.3.1 7 days Post Procedure(-3/+10)

1. Interim history and physical examination
2. Cardiac Medications
3. Chest X-Ray

5.3.2 90 days post procedure (-15/+15)

1. Interim history and physical examination
2. Cardiac Medications
3. Chest X-Ray

5.3.3 180 days Post Procedure (-30/+30)

1. Interim history and physical examination
2. Cardiac Medications
3. Chest X-Ray

4. Either Cardiac computed tomography angiography (CCTA) or Transesophageal Echocardiogram (TEE) to be completed to confirm LAA closure

6. MATRIX

	Screening /Baseline	Procedure	7 Day Follow-up (-3/+10)	90 Day Follow-up (-15/+15)	180 Day Follow-up (-30/+30)
History & Physical	X				
EP Consultation	X				
Cardiac Medication	X		X	X	X
Labs: Creatinine & BUN	X				
CHADS2-VASC Score	X				
HAS-BLED Score	X				
Chest X-Ray			X	X	X
TEE		X			X*
CCTA	X				X*
Angiography		X			
Adverse Events Assessment		X	X	X	X

*Either a CCTA or TEE will be completed to confirm LAA closure

7. SUMMARY

7.3.1 **Enrollment:** up to 50 subjects to be enrolled

7.3.2 **Duration of Enrollment:** 180 days (-30/+30)

8. SCREENING

Subjects evaluated for left atrial appendage closure will be screened for inclusion and consented prior to their procedure. During clinical evaluation of the patient, the physician investigator will assess those items described in Table 1. If the anatomy is favorable for placement of the Lariat® device, the procedure will be performed at one of the participating centers. If anatomy is not favorable, the patient will be excluded from the study and managed using best care practices by his or her physician.

A copy of the consent form will be given to the patient and another copy will be placed in the patients chart along with documentation of the consent process.

9. ENROLLMENT

Subjects consented will be tracked by the study team and will be considered enrolled in this study at the time of the start of their left atrial appendage closure procedure. All subjects that are consented who do not undergo left atrial appendage closure with SentreHeart Lariat® will be considered screen failures. Any patients that have a failed attempt at left atrial appendage closure with SentreHeart Lariat® will be tracked through their index hospitalization for safety; their study follow up will be complete at the time of discharge.

Subjects that are approached will be given ample time to assure that this population has the opportunity to carefully read the consent, share the information with family members, and discuss the objective of the study along with any risks/benefits that may be expected. Subjects will have all of their questions answered before signing the consent and taking part in the study. Additionally, information on how to contact the study doctor will be provided in the consent form.

9.3 Screening/Enrollment Log

A log will be maintained that documents subjects screened and those enrolled.

10. WITHDRAWAL

A subject may voluntarily withdraw at any time.

11. END OF STUDY

Enrollment in this study will be completed once a subject completes all of the protocol required 90 day assessments. If a subject is unable to complete these assessments, their enrollment will be completed at the end of the 90 day window unless an appointment has been made to complete an out of window visit for extenuating circumstances. Any patients that have a failed attempt at left atrial appendage closure with SentreHeart Lariat® will be tracked through their index hospitalization for safety; their study follow up will be complete at the time of discharge.

If unsuccessful attempts have been documented to contact and arrange an end of study follow-up visit (90 day), the social security death index will be queried at a later date to confirm the subjects' status at the time of study completion.

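### Section 11 ends participation at the 90-day visit while the schedule runs to 180 days; applied as written, it drops the only protocol-scheduled closure image after the procedure day

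*Combined protocol and SAP*

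**What the plan says.** Section 11 sets the exit rule for a treated subject, and names 90 days three times:

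- On completing assessments: "Enrollment in this study will be completed once a subject completes all of the protocol required 90 day assessments".
- If the assessments cannot be done: "their enrollment will be completed at the end of the 90 day window unless an appointment has been made" for an out-of-window visit.
- On subjects who cannot be reached, where the final visit is labelled as the 90-day one: if attempts fail to "arrange an end of study follow-up visit (90 day), the social security death index will be queried".

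Other sections run to 180 days:

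- Section 3: "Patients will undergo follow-up visits at 7 days, 90 days, and 180 days post procedure".
- Section 5.3.3, under the 180-day visit only: "Either Cardiac computed tomography angiography (CCTA) or Transesophageal Echocardiogram (TEE) to be completed to confirm LAA closure".
- Section 6, footnote to the TEE and CCTA entries in the 180-day column: "Either a CCTA or TEE will be completed to confirm LAA closure". The same column carries an adverse event assessment.
- Section 7.3.2 gives the duration of enrollment as 180 days with a tolerance of 30 days either side.

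Closure is also assessed during the procedure. Section 5.2 lists "TEE evidence of LAA closure" and "Angiographic confirmation of LAA closure". Section 2 names adverse events and closure rates as secondary aims. Section 15 reports closure as a percentage and gives no time point.

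**The concern.** A site looking for the rule on when a subject is finished would turn to the section headed End of Study. There it would find that the subject is finished at 90 days. A site working from the visit schedule would keep the subject to 180 days. Nothing in the document says which prevails.

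The difference matters because closure is imaged on the procedure day and then not again until day 180. The 7-day and 90-day visits have a chest X-ray but no TEE or CCTA, and the baseline CCTA is an anatomy check before the procedure. Ending participation at 90 days therefore removes all scheduled evidence on whether the appendage stayed closed. It also removes the last scheduled adverse event assessment. In a multi-center registry, sites that read the document differently would follow their subjects for different lengths of time, and the denominator for closure at follow-up would depend on which section each site followed.

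**Working it through.** The plan gives no sample-size or power figure that bears on this point, so there is nothing of that kind to reproduce. The check sets the passages side by side and works out the visit windows.

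**1. Windows (Sections 5.3.2 and 5.3.3).**
- 90-day visit, -15/+15: 90 - 15 = day 75 to 90 + 15 = day 105.
- 180-day visit, -30/+30: 180 - 30 = day 150 to 180 + 30 = day 210.

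**2. Gap between a Section 11 exit and the 180-day window.**
- Latest in-window exit: 150 - 105 = 45 days before the window opens.
- Earliest in-window exit: 150 - 75 = 75 days before it opens.

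The windows do not overlap, so no in-window 90-day visit can also serve as the 180-day visit.

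**3. What each rule leaves, per successfully treated subject (Sections 5.2, 5.3 and 6).**

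| Item | Schedule to 180 days | Section 11 applied |
|---|---|---|
| Follow-up visits | 3 (days 7, 90, 180) | 2 (days 7, 90) |
| Adverse event assessments | 4 (procedure, days 7, 90, 180) | 3 |
| Scheduled closure images after the procedure day | 1 (day 180) | 0 |
| Closure assessments on the procedure day | 2 (TEE, angiography) | 2 |

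**4. Nominal follow-up time.** With the maximum of 50 subjects all followed, 50 × 180 / 365.25 = 24.6 patient-years, against 50 × 90 / 365.25 = 12.3. Both are upper bounds, since they ignore failed attempts and dropout.

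**5. Readings that might remove the conflict.**
- *Section 11 is about accrual to the study.* It is not. It speaks of an individual subject completing assessments.
- *Section 7.3.2 is about accrual.* This is possible, because the line follows the enrollment count. However, its tolerance is the same as that of the 180-day visit, so a per-subject duration is more likely. Without Section 7.3.2, Sections 3, 5.3.3 and 6 still contradict Section 11.
- *The out-of-window exception keeps the subject in.* It covers only subjects who could not complete the 90-day assessments, and those include no TEE or CCTA.
- *A slip of the pen.* The 90-day end point appears three times in Section 11, so it is not a single typing error.

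**The case against.** The strongest reply is that the harm is conditional. The images are lost only if a site follows Section 11 over the design section, the itemised visit list and the matrix, and nothing in the document shows that any site would. The study is descriptive, with up to 50 patients, no power calculation and no endpoint tied to a follow-up time. Section 15 can still be satisfied with a percentage from the procedure-day TEE and angiography, so no stated analysis becomes impossible. Nor does the protocol rule out other imaging done for clinical reasons. On this view the point is a drafting inconsistency, worth correcting but not critical.

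Much of this is fair. The defect is an internal inconsistency, not a poor design decision. Procedure-day closure survives, and the missing time point in Section 15 is a separate weakness. The death-index point also needs care. If participation really ends at 90 days, a subject cannot be lost afterwards. A gap in vital status arises only if follow-up runs to 180 days while the query stays tied to the 90-day visit.

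The reply does not remove the contradiction. The conditional loss falls on both secondary aims, and a closure image missed at 180 days cannot be obtained later for that time point.

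**Conclusion.** The concern holds. Section 11 contradicts Sections 3, 5.3.3 and 6, and probably Section 7.3.2, and no text resolves the conflict. If Section 11 is applied, a subject who completes the 90-day visit in window leaves 45 to 75 days before the 180-day window opens. The protocol then has no scheduled evidence of closure after the procedure day.

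This affects at most 50 subjects. The number is smaller if any closure attempts fail, because those subjects leave at discharge under Sections 5, 9 and 11 and would not reach the 180-day image in any case. The conclusion rests on reading Section 11 as written; it does not assume that any site has ended follow-up early. It should be corrected before the plan is relied on, because which rule is followed decides whether protocol-scheduled closure data at follow-up exist at all.

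**What to change.** The sponsor should state which end of study is intended and reconcile Section 11 with Sections 3, 5.3.3, 6 and 7.3.2. The visit schedule and its imaging point to 180 days. If that is confirmed:

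- Change the three 90-day references in Section 11 (completion of assessments, close of the window, and the end-of-study visit) to the 180-day visit and its window of days 150 to 210.
- Tie the death-index query to that same visit, so that a subject lost between the 90-day and 180-day visits also has vital status checked.

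If 90 days is intended instead, Sections 3, 5.3.3, 6 and 7.3.2 need amending, and the plan should say that closure will be reported for the procedure day only.

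The cost is sponsor confirmation and a wording amendment. With 180 days confirmed, no visit or image is added to the schedule, though any site that had been ending participation at 90 days would have to start carrying them out. The consent pages were not available for this review, so the duration they give should be checked against the amended text.

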15 STATISTICAL ANALYSIS & DATA MANAGEMENT

Data on the clinical and non-clinical risk factors will be summarized using means, standard deviations (SDs) and percentages. Successful left atrial appendage closure will be reported as a percentage

Table 1. Patient screening tool

1. Atrial fibrillation or atrial flutter documented? Yes No
 Paroxysmal Short-lasting persistent Longstanding persistent

2. EP consultation to exclude candidacy for ablation? Yes No
 catheter or surgical

3. CTA obtained to assess LAA anatomy? Yes No
 If yes, was anatomy favorable for this procedure? Yes No
 If no, justification for procedure:

If no, was second opinion obtained? Yes No
 Physician rendering second opinion: _____

4. CHADS₂-VASC score _____ of 9
 a. CHF _____ of 1
 b. Hypertension _____ of 1
 c. Age >65 yrs _____ of 1
 d. Diabetes Mellitus _____ of 1
 e. Stroke or TIA _____ of 2
 f. Vascular Disease _____ of 1
 g. Age >75 _____ of 1 (in addition to age>65)
 h. Sex Category _____ of 1 (Male=0; Female =1)

5. CHADS₂ score: _____ of 6
 a. CHF _____ of 1
 b. Hypertension _____ of 1
 c. Age >75 yrs _____ of 1
 d. Diabetes Mellitus _____ of 1
 e. Stroke or TIA _____ of 2

6. HAS-BLED SCORE _____ of 9
 a. Hypertension _____ 1
 b. Abnormal renal and hepatic function ² _____ 1-2
 c. Stroke _____ 1
 d. Bleeding tendency/predisposition³ _____ 1
 e. Labile INRs on warfarin⁴ _____ 1

¹Systolic BP >160 mmHg

²Renal: serum creatinine >2.25 mg/dl
 Hepatic: Bili 2-3x normal and
 AST/ALT/ALK-P >3x normal or chronic
 disease (cirrhosis)

³History of bleeding or anemia

⁴Time in therapeutic range <60%

⁵Concomitant antiplatelet or NSAID use or
 excess alcohol

f. Elderly (>65 yr) 1
g. Drugs or alcohol (1 point each)⁵ 1-2

6. If CHADS₂-VASC score<3, or if HAS-BLED score is <3, list justification for procedure:

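### Failed Lariat attempts count as enrolled but leave the study at discharge, so their later strokes, deaths, bleeding and complications have no planned ascertainment

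*Combined protocol and SAP*

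**What the plan says.** Sections 5 and 9 fix the moment of enrollment: consented subjects "will be considered enrolled in this study at the time of the start of their left atrial appendage closure procedure". Both sections then add that "All subjects that are consented who do not undergo left atrial appendage closure with SentreHeart Lariat® will be considered screen failures". A separate sentence on failed attempts, repeated in Sections 5, 9 and 11, has them "tracked through their index hospitalization for safety; their study follow up will be complete at the time of discharge".

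For the study generally, Section 3 states: "Patients will undergo follow-up visits at 7 days, 90 days, and 180 days post procedure". The Section 6 matrix schedules an adverse-event assessment at the procedure and at each of those three visits. Section 11 provides one passive check on vital status. It applies when attempts fail to arrange an "end of study follow-up visit (90 day), the social security death index will be queried at a later date".

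Section 2 makes the outcome of patients undergoing the procedure the primary aim and adds: "Secondary aims include assessment of adverse events and successful LAA closure rates". On analysis, Section 15 says that clinical and non-clinical risk factors will be summarized descriptively and that "Successful left atrial appendage closure will be reported as a percentage". It names no denominator for adverse events and no rule for missing data.

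**The concern.** Whether a patient is observed after discharge is decided by the procedural result, which is itself a study outcome. Events during the index stay are captured for everyone. Events after discharge are sought only in patients whose closure did not fail.

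Two kinds of post-discharge rate could then be reported. A rate over all enrolled subjects treats unobserved failures as event-free, and is too low if any of them has an event. A rate among successes alone flatters the device if failures fare worse. That is plausible: the appendage remains open, Section 4 describes the population as one in which oral anticoagulation is contraindicated, and Section 1 says of patients with clinically significant bleeding, intracranial hemorrhage or a prohibitive fall risk that they "often do not receive OAC therapy, and remain at elevated risk for stroke". That sentence is not about failed Lariat attempts, however, and the documents do not show that failures do worse.

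It is also unclear whether failed attempts enter any rate at all, because the screen-failure sentence can be read as removing them.

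**Working it through.** **Text check**

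1. *Are failed attempts enrolled?* Enrollment occurs when the procedure starts (Sections 5 and 9), so a started attempt that fails is enrolled. The screen-failure sentence and the Section 3 cohort definition, which refers to patients who undergo Lariat closure, allow another reading. The separate sentence giving failed attempts their own follow-up rule favors treating them as enrolled. On the other reading they also leave the denominator, which makes the problem worse.
2. *Does anything collect their later events?* Section 5.3 and the Section 6 matrix schedule visits, but the failed-attempt rule ends follow-up before them. The death-index query in Section 11 is triggered by an end-of-study visit that cannot be arranged, and failed attempts have no such visit. Section 12.1 covers review, adjudication and reporting of adverse events, and adds no collection after discharge. Spontaneous reports might arrive, but they are not planned ascertainment.

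**Illustration of size**

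The plan has no figure to reproduce. It gives a cap of 50 subjects (Sections 3, 4 and 7) and no failure or event rate. Inputs:

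- n = 50 attempts, from the documents.
- f = 1, 5 or 10 failures: assumption.
- Post-discharge event risk after success, ps = 5%: assumption.
- Post-discharge event risk after failure, pf = 5%, 10% or 20%: assumption.

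Formulas:

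- Expected missed events = f × pf
- All-attempt rate = [(50 − f) × 0.05 + f × pf] / 50
- Rate recorded over all 50 = (50 − f) × 0.05 / 50
- Width of the undetermined range = f / 50, from no failed patient having an event to every one having an event

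| f | Recorded over 50 | All-attempt rate (pf = 5 / 10 / 20%) | Missed events (pf = 5 / 10 / 20%) | Width f/50 |
|---|---|---|---|---|
| 1 | 2.45/50 = 4.9% | 2.50, 2.55, 2.65 of 50 = 5.0 / 5.1 / 5.3% | 0.05 / 0.1 / 0.2 | 2 points |
| 5 | 2.25/50 = 4.5% | 2.50, 2.75, 3.25 of 50 = 5.0 / 5.5 / 6.5% | 0.25 / 0.5 / 1.0 | 10 points |
| 10 | 2.00/50 = 4.0% | 2.50, 3.00, 4.00 of 50 = 5.0 / 6.0 / 8.0% | 0.5 / 1.0 / 2.0 | 20 points |

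The rate among successes is 5.0% in every row, so it equals the all-attempt rate when pf = ps.

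The chance of missing at least one event is 1 − (1 − pf)^f. At pf = 10% this is 1 − 0.9 = 10%, 1 − 0.9^5 = 41% and 1 − 0.9^10 = 65% for 1, 5 and 10 failures.

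As a concrete bound, suppose 2 events are seen among the followed patients. The all-attempt proportion then lies between 2/50 and (2 + f)/50: 4–6%, 4–14% and 4–24% for f = 1, 5 and 10.

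**The case against.** The strongest reply is that this is a deliberate and disclosed choice. The rule is stated three times, and in-hospital safety is kept. The study is a single-arm descriptive registry with no hypothesis test and no event-rate target. Section 3 defines the cohort by undergoing closure, so the long-term target may fairly be patients whose appendage was closed, with failures contributing procedural safety and the closure percentage. The understatement over all 50 arises only from a denominator the plan never specifies, and the successes-only rate is unbiased under equal risk. Every rate above is assumed, and the f/50 width is the algebraic worst case. The death-index query is consistent with the plan's own rule, since a failed attempt completes the study at discharge, when status is known. Finally, failed patients may go on to other management, so later events would not be cleanly attributable to the device.

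Much of this stands as a limit on size. The direction and amount of bias cannot be established from the documents, and the death-index point shows only that there is no backstop; it is not a second fault. The objection does not remove the gap. Section 2 aims at the outcome of patients undergoing the procedure, and failed attempts underwent it. Restricting the target to successful closures would be a defensible choice, but the plan does not state it and its enrollment rule points the other way. Imperfect attribution is a reason to report by procedural result. It is not a reason to leave the events uncollected.

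**Conclusion.** The concern holds. No part of the plan collects events after discharge in failed attempts, although the plan's own definition makes them enrolled subjects. As written, it cannot give post-discharge outcomes for all patients undergoing the procedure.

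Confidence is high that the gap exists, and does not extend to its size or direction. Under the stated assumptions the shortfall in a rate over all 50 runs from 0.1 percentage points (1 failure, 5% risk: 5.0% against 4.9%) to 4 points (10 failures, 20% risk: 8.0% against 4.0%). With one failure it hardly matters; with several, it could change how a 50-patient registry is read. The plan should be changed, because the correction is cheap and data not collected after discharge may not be recoverable later.

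**What to change.** 1. In Sections 5, 9 and 11, replace the end of follow-up at discharge with clinic or telephone contact, without study imaging, for adverse events, stroke or TIA, bleeding and vital status, at the same time points as other subjects.
2. In Section 11, extend the death-index query to failed attempts who cannot be contacted.
3. In Sections 5 and 9, limit screen failures to consented subjects whose procedure was not started, so that every started procedure stays in the denominator.
4. In Section 15, report adverse events over all procedures started and separately by procedural result. This needs a definition of a failed attempt, for example whether it covers incomplete closure as well as an abandoned procedure; the documents give none.
5. Reconcile the 90-day end of study in Section 11 with the 180-day schedule in Sections 3, 5.3, 6 and 7, and apply the reconciled horizon to failed attempts too. The main point does not depend on this item.

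**Cost.** Up to three extra contacts per failed attempt (3, 15 or 30 in total for 1, 5 or 10 failures), the coordinator time for them, and matching consent wording. Events detectable only by chest X-ray would still be less completely ascertained in failed attempts than in successes, and the report of results should say so.
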